5.1. Summary of Study Design

This is a Phase 1, multi-center, open-label, single dose study to determine the pharmacokinetic (PK), safety, and tolerability of lasmiditan in pediatric patients with a diagnosis of migraine.

Two cohorts will be evaluated:

- Primary **Cohort 1**: 15 kg to ≤ 40 kg
- Secondary **Cohort 2**: >40 kg to ≤ 55 kg

The planned doses for Cohorts 1 and 2 are 100 mg and 200 mg, respectively.

Study Period I (Screening)

All patients are screened to determine if they are eligible to participate in the study.

Screening will occur 28 days to 3 days prior to lasmiditan dosing.

Study Period II (PK Assessment/Safety)

Enrolled patients and the patient's parent or guardian will receive instructions regarding study procedures prior to dosing, including fasting requirements.

Day 1:

- Patients arrive at the Clinical Research Unit (CRU) for assessments prior to dosing.
- Patients receive the single lasmiditan dose.
- Patients can go home after the 12-hour assessments. Patients may be offered the opportunity to spend the night depending on CRU capabilities.

Day 2:

- Patient assessments are done at the CRU approximately 24 hours after dosing.

Study Period III (Follow-Up Period)

Patients return to the CRU for a follow-up visit approximately 14 days after dosing.

5.2. Determination of Sample Size

For the primary cohort (body weight between 15 and ≤ 40 kg, inclusive), approximately 13 patients may be enrolled to obtain at least 11 patients with evaluable PK data. Patients who do not have evaluable PK data may be replaced.

From the population PK analysis in adults, the inter-patient coefficient of variation was estimated to be 43% for C_{max} and 39% for AUC. Assuming the coefficient of variation of total variability is not larger than 45%, 11 pediatric patients will provide at least 80% coverage probability that the 95% confidence interval (CI) for the geometric mean of these key PK parameters will be within 70% and 140%. The coefficient of variation for apparent total body clearance and

apparent central volume of distribution are similar and, therefore, the precision of estimates for these parameters are expected to be sufficient.

Moreover, approximately 8 patients (body weight >40 kg and ≤55 kg) in the secondary cohort may be enrolled to obtain at least 6 patients with evaluable PK data. This sample size is customary for Phase 1 studies evaluating PK, safety, and tolerability, and is not powered on the basis of statistical hypothesis testing.

Efforts will be made to enroll female and male patients of varying body weights across the weight range defined for the primary and secondary cohorts.

5.3. Method of Assignment to Treatment

Patients who meet all criteria for enrollment at Visit 2 will receive an open label dose of lasmiditan 200 mg or lasmiditan 100 mg, according to their body weight, as shown in [Table LAHX.5.1](#) below.

Table LAHX.5.1. Planned Treatment Regimen

Cohort	1	2
Participant Body Weight	15 kg to ≤40 kg	>40 kg to ≤55kg
Treatment Name	Lasmiditan	lasmiditan
Dosage Formulation	Tablet	Tablet
Unit dose strength(s)/Dosage Level(s)	50 mg x2 or 100 mg x1	50 mg x4 or 100 mg x2
Route of Administration	Oral	Oral
Dosing instructions	With approximately 240 mL of room temperature water in a sitting position	

6. A Priori Statistical Methods

6.1. General Considerations

Data listings will be provided for all data that is databased, and will be presented by cohort. Summary statistics and statistical analysis will only be presented for data where detailed in this SAP. For continuous data, summary statistics will include the arithmetic mean, arithmetic standard deviation (SD), median, minimum, maximum and number of patients that provided data (N). For log-normal data (eg, the PK parameters: AUCs and C_{max}), the geometric mean and the corresponding 95% CI, and geometric CV% will also be presented. For categorical data, frequency count and percentages will be presented. Data listings will be provided for all patients up to their last collected measurement, and will highlight patients who discontinue from the study before follow-up. For the calculation of summary statistics and statistical analysis, unrounded data will be used.

Change from baseline values will be calculated for laboratory data, vital signs data, and Cogstate Pediatric Brief Battery data. Each individual change from baseline will be calculated by subtracting the individual patient's baseline value from the value at the timepoint. Mean change from baseline is the mean of all individual patients' change from baseline values. The individual patients' change from baseline values will be used to calculate the mean change from baseline using a SAS procedure such as Proc Univariate.

Individual derived parameters (eg, PK parameters) and appropriate summary statistics will be reported to 3 significant figures. Observed concentration data, eg, C_{max} , should be reported as received. Observed time data, eg, t_{max} , should be reported as received. Observed safety data should be reported as received. Counts should be reported as whole numbers and percentage values should be reported to 1 decimal place. Median values should be treated as an observed parameter and reported to the same number of decimal places as minimum and maximum values.

Pharmacokinetic analyses will be conducted on data from all patients who receive a dose of the investigational product and have evaluable PK data. Patients may be excluded from the PK summary statistics and statistical analysis if a patient has an adverse event (AE) of vomiting that occurs at or before 2 times median time of maximum observed drug concentration (t_{max}).

Safety analyses will be conducted for all enrolled patients who receive a dose of the investigational product, whether or not they completed all protocol requirements.

Pharmacokinetic data analyses will be presented by:

- body weight category (15 kg to ≤ 40 kg, >40 kg to ≤ 55 kg)
- age category (6 to <12 years of age, 12 to <18 years of age)
- body surface area (0.65 m² to ≤ 1.3 m², >1.3 m² to ≤ 1.6 m²)
- glomerular filtration rate (<75 mL/min/1.73 m², ≥ 75 mL/min/1.73 m²)
- region (Japan, US), if appropriate

Safety data analyses will be presented by body weight category or age category, as appropriate.

All protocol deviations that occur during the study will be considered for their severity/impact and will be taken into consideration when PK and safety analyses are conducted.

Data analysis will be performed using SAS[®] Version 9.4 or greater.

6.2. Handling of Dropouts or Missing Data

Missing data will not be displayed in listings.

Some of the tables, figures, and listings (TFLs) may not have sufficient numbers of patients or data for presentation. If this occurs, the blank TFL shell will be presented with a message printed in the center of the table, such as, “No serious adverse events occurred for this study”.

6.3. Extent of Exposure

Dosing details for each patient will be displayed in a listing.

6.4. Patient Disposition

Patient disposition will be displayed in a listing.

6.5. Patient Characteristics

6.5.1. Demographics

The following patient characteristics at screening will be summarized for all enrolled patients who receive a dose of the investigational product, and presented by body weight category and age category:

- Age (continuous variable)
- Sex (Male, Female)
- Race (American Indian or Alaska Native, Asian, Black or African American, Native Hawaiian or Other Pacific Islander, Caucasian, Multiple, Other)
- Ethnicity (Hispanic or Latino, Not Hispanic or Latino)
- Height (cm) (continuous variable)
- Weight (kg) (continuous variable)
- Average number of attacks per month in the last 2 months (continuous variable)
- Body mass index (BMI) ($\text{weight (kg)} / [\text{height (m)}]^2$) (continuous variable)
- Body surface area (0.65 m^2 to $\leq 1.2 \text{ m}^2$, $> 1.2 \text{ m}^2$ to $\leq 1.6 \text{ m}^2$) (Sharkey et al. 2001)
- Glomerular filtration rate ($< 75 \text{ mL/min/1.73 m}^2$, $\geq 75 \text{ mL/min/1.73 m}^2$) (Pottel et al. 2015)
- Menstrual status for female patients (Pre-menarchal, Menarchal)
- Pubertal status (Prepubertal, Pubertal)

Age will be calculated using the difference in days between the date of birth and the date of informed consent.

Body surface area (m^2) will be calculated as: $0.03330 * W^{(0.6157-0.0188\log_{10}(W))} * H^{0.3}$, where W is weight (kg) and H is height (cm) (Boyd 1935).

Height will be measured in triplicate and the mean value will be recorded.

Glomerular filtration rate will be calculated using the Bedside Schwartz formula: $0.413 * (\text{height [cm]} / \text{serum creatinine [mg/dL]})$ (Schwartz et al. 2009).

All demographic data will be presented in a listing. For Japanese patients, glomerular filtration rates in this listing will be calculated using both the Bedside Schwartz formula and the Japanese Society for Pediatric Nephrology formula: $110.2 * (\text{reference serum creatinine [mg/dL]} / \text{patient serum creatinine [mg/dL]}) + 2.93$ (Uemura 2015).

6.6. Pharmacokinetic Assessment

6.6.1. Pharmacokinetic Analysis

Pharmacokinetic parameter estimates will be determined using non-compartmental procedures in validated software program (Phoenix WinNonlin Version 6.4 or later). Pharmacokinetic analysis using a compartmental modeling approach will be described in a separate PK/pharmacodynamic analysis plan document.

Plasma concentrations of lasmiditan will be used to determine the following PK parameters, when possible:

Parameter	Units	Definition
C_{\max}	ng/mL	maximum observed drug concentration
t_{\max}	h	time of maximum observed drug concentration
AUC(0- ∞)	ng.h/mL	area under the concentration versus time curve from time zero to infinity
AUC(0- t_{last})	ng.h/mL	area under the concentration versus time curve from time zero to time t, where t is the last time point with a measurable concentration
%AUC(t_{last} - ∞)	%	percentage of AUC(0- ∞) extrapolated
$t_{1/2}$	h	half-life associated with the terminal rate constant (λ_z) in non-compartmental analysis
CL/F	L/h	apparent total body clearance of drug calculated after extra-vascular administration
V_z/F	L	apparent volume of distribution during the terminal phase after extra-vascular administration
V_{ss}/F	L	apparent volume of distribution at steady state after extra-vascular administration

Additional PK parameters may be calculated, as appropriate. The software and version used for the final analyses will be specified in the clinical study report. Any exceptions or special handling of data will be clearly documented within the final study report.

Formatting of tables, figures, and abbreviations will follow the Eli Lilly and Company (Lilly) Global PK/PD/TS Tool: NON-COMPARTMENTAL PHARMACOKINETIC STYLE GUIDE. The version of the tool effective at the time of PK analysis will be followed.

General PK Parameter Rules

- Actual sampling times will be used in the final analyses of individual PK parameters, except for non-bolus pre-dose sampling times which will be set to zero. For non-bolus, multiple dose profiles, the pre-dose time will be set to zero unless a time deviation falls outside of the protocol blood collection time window which is considered to impact PK parameter derivation.
- C_{\max} and t_{\max} will be reported from observed values. If C_{\max} occurs at more than 1 time point, t_{\max} will be assigned to the first occurrence of C_{\max} .
- AUC parameters will be calculated using a combination of the linear and logarithmic trapezoidal methods (linear-log trapezoidal rule). The linear trapezoidal method will be applied up to t_{\max} and then the logarithmic trapezoidal method will be used after t_{\max} . The minimum requirement for the calculation of AUC will be the inclusion of at least 3 consecutive plasma concentrations above the lower limit of quantification, with at least 1 of these concentrations following C_{\max} . AUC(0- ∞) values where the percentage of the total area extrapolated is more than 20% will be flagged. Any AUC(0- ∞) value excluded from summary statistics will be noted in the footnote of the summary table.

- Half-life ($t_{1/2}$) will be calculated, when appropriate, based on the apparent terminal log-linear portion of the concentration-time curve. The start of the terminal elimination phase for each patient will be defined by visual inspection and generally will be the first point at which there is no systematic deviation from the log-linear decline in plasma concentrations. Half-life will only be calculated when a reliable estimate for this parameter can be obtained comprising of at least 3 data points. If $t_{1/2}$ is estimated over a time window of less than 2 half-lives, the values will be flagged in the data listings. Any $t_{1/2}$ value excluded from summary statistics will be documented in the footnote of the summary table.
- A uniform weighting scheme will be used in the regression analysis of the terminal log-linear portion of the concentration-time curve.
- The parameters based on predicted concentration at last quantifiable timepoint will be reported.

Individual PK Parameter Rules

- Only quantifiable concentrations will be used to calculate PK parameters with the exception of special handling of certain concentrations reported below the lower limit of quantitation (BQL). Plasma concentrations reported as BQL will be set to a value of zero when all of the following conditions are met:
 - The compound is non-endogenous.
 - The samples are from the initial dose period for a patient or from a subsequent dose period following a suitable wash-out period.
 - The time points occur before the first quantifiable concentration.
- All other BQL concentrations that do not meet the above criteria will be set to missing.
- In addition, where 2 or more consecutive concentrations are BQL towards the end of a profile, the profile will be deemed to have terminated and therefore any further quantifiable concentrations will be set to missing for the calculation of the PK parameters unless it is considered to be a true characteristic of the profile of the drug.

Individual Concentration vs. Time Profiles

- Individual concentrations will be plotted utilizing actual sampling times.
- The terminal point selections will be indicated on a semi-logarithmic plot.

Average Concentration vs. Time Profiles

- The average concentration profiles will be graphed using scheduled (nominal) sampling times.
- The average concentration profiles will be graphed using arithmetic average concentrations.
- The pre-dose average concentration for single-dose data from non-endogenous compounds will be set to zero. Otherwise, only quantifiable concentrations will be used to calculate average concentrations.
- Concentrations at a sampling time exceeding the sampling time window specified in the protocol, or $\pm 10\%$, will be excluded from the average concentration profiles.

- Concentrations excluded from the mean calculation will be documented in the final study report.
- A concentration average will be plotted for a given sampling time only if 2/3 of the individual data at the time point have quantifiable measurements that are within the sampling time window specified in the protocol or $\pm 10\%$. An average concentration estimated with less than 2/3 but more than 3 data points may be displayed on the mean concentration plot if determined to be appropriate and will be documented within the final study report.

Treatment of Outliers during Pharmacokinetic Analysis

Application of this procedure to all PK analyses is not a requirement. Rather, this procedure provides justification for exclusion of data when scientifically appropriate. This procedure describes the methodology for identifying an individual value as an outlier for potential exclusion, but does not require that the value be excluded from analysis. The following methodology will not be used to exclude complete profiles from analysis.

Data within an Individual Profile

A value within an individual profile may be excluded from analysis if any of the following criteria are met:

- For PK profiles during single dosing of non-endogenous compounds, the concentration in a pre-dose sample is quantifiable.
- For any questionable datum that does not satisfy the above criteria, the profile will be evaluated and results reported with and without the suspected datum.

Data between Individual Profiles

1. If $n < 6$, then the dataset is too small to conduct a reliable range test. Data will be analyzed with and without the atypical value, and both sets of results will be reported.
2. If $n \geq 6$, then an objective outlier test will be used to compare the atypical value to other values included in that calculation:
 - a. Transform all values in the calculation to the logarithmic domain.
 - b. Find the most extreme value from the arithmetic mean of the log transformed values and exclude that value from the dataset.
 - c. Calculate the lower and upper bounds of the range defined by the arithmetic mean $\pm 3 \times SD$ of the remaining log-transformed values.
 - d. If the extreme value is within the range of arithmetic mean $\pm 3 \times SD$, then it is not an outlier and will be retained in the dataset.
 - e. If the extreme value is outside the range of arithmetic mean $\pm 3 \times SD$, then it is an outlier and will be excluded from analysis.

If the remaining dataset contains another atypical datum suspected to be an outlier and $n \geq 6$ following the exclusion, then repeat step 2 above. This evaluation may be repeated as many

times as necessary, excluding only 1 suspected outlier in each iteration, until all data remaining in the dataset fall within the range of arithmetic mean $\pm 3 \times \text{SD}$ of the log-transformed values.

Reporting of Excluded Values

Individual values excluded as outliers will be documented in the final report. Approval of the final report will connote approval of the exclusion.

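### SAP 6.6.1 conflicts with itself on whether a flagged PK value must be dropped and, at the planned cohort sizes, promises no result with the value kept (minor, cheap to fix)

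*SAP*

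**What the plan says.** Only the SAP bears on this point, since the protocol addendum has no pharmacokinetic analysis (Protocol 4.15 and 4.16.3).

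- **Status of the procedure** (SAP 6.6.1, Treatment of Outliers, preamble). "Application of this procedure to all PK analyses is not a requirement"; rather, "this procedure provides justification for exclusion of data when scientifically appropriate". It identifies candidates "but does not require that the value be excluded from analysis". Complete profiles may not be removed by it.
- **Between profiles, n < 6** (step 1). "Data will be analyzed with and without the atypical value, and both sets of results will be reported".
- **Between profiles, n ≥ 6** (step 2). "an objective outlier test will be used to compare the atypical value to other values included in that calculation". The most extreme log value is set aside, and the bound is the mean ± 3 SD of the rest. Under step 2e, a value beyond the bound is declared an outlier in these words: "then it is an outlier and will be excluded from analysis". The step may be repeated while at least six values remain.
- **Reporting.** "Individual values excluded as outliers will be documented in the final report". No summary with the value kept is promised for n ≥ 6.
- **Within a profile.** A doubtful value that does not meet the exclusion criterion is reported both ways. A quantifiable pre-dose value falls under a permissive rule ("A value within an individual profile may be excluded from analysis if any of the following criteria are met") with no parallel result. The contrast drawn here is therefore confined to the between-profile rule.
- **Sizes** (SAP 5.2). The primary cohort has about 13 enrolled for at least 11 evaluable; the secondary has about 8 for at least 6.

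**The concern.** The geometric mean, its 95% confidence interval and the geometric CV of Cmax and AUC are the summaries that answer the SAP's primary objective (SAP 4 and 6.6.2). Two analysts could follow Section 6.6.1 in good faith and report different summaries. One would read step 2e as binding; the other would read the preamble as leaving the choice open. For between-profile values, neither what counts as atypical nor what counts as scientifically appropriate is defined.

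The step that carries the binding wording is also the one without a parallel result, and it is the step that applies at both planned cohort sizes. A 3 SD limit sounds like a rare-event limit. At 6 to 13 values, with the tested value left out of the SD, it is not. If a valid value is dropped, the interval is too narrow and the variability too low, and no promised table would show by how much.

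**Working it through.** **1. The plan's own figure.** SAP 5.2 assumes a total CV of at most 45% and claims at least 80% probability that, with 11 patients, the 95% interval lies within 70–140%.

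- Log SD = √ln(1 + 0.45²) = 0.429.
- Log half-width = t(0.975, n−1) × s/√n, which must stay below ln 1.4 = 0.336 (the tighter side, since −ln 0.7 = 0.357).
- Simulated probability, with limits taken relative to the estimated geometric mean: 80.8% at n = 11 and 71.0% at n = 10.

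The stated figure is reproduced. The SAP gives no error rate for the outlier test, so there is none to reproduce.

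**2. How often the bound flags clean data.** For one normal log value against the other n−1, the standardised distance exceeds 3 SD with two-sided probability 2·P(t with n−2 df > 3/√(1 + 1/(n−1))). The most extreme of n is tested, so multiply by n.

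| n | t cut-off | per value | × n | simulated |
|---|---|---|---|---|
| 6 | 2.74 | 0.0520 | 31.2% | 31.3% |
| 8 | 2.81 | 0.0309 | 24.7% | 24.8% |
| 11 | 2.86 | 0.0188 | 20.6% | 20.6% |
| 13 | 2.88 | 0.0149 | 19.4% | 19.3% |

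The rate does not depend on the CV. The same bound, expressed in ordinary SDs from the mean of all n values, is G = [3(n−1)/n] / √{[(n−2) + 9(n−1)/n]/(n−1)}. At n = 6 this is 2.5/√(11.5/5) = 1.65. At n = 8, 11 and 13 it is 1.86, 2.08 and 2.18.

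**3. What exclusion does to the summary.** Log-normal data were simulated at CV 45%, with step 2 repeated while n ≥ 6 and a t-based 95% interval on the retained values. The worst case means that every dataset is tested and every flag is acted on.

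| | n = 6 | 8 | 11 | 13 |
|---|---|---|---|---|
| Coverage, nothing excluded | 95% | 95% | 95% | 95% |
| Coverage, worst case, all datasets | 88% | 88% | 90% | 91% |
| Coverage, only datasets where a valid value is dropped | 72% | 66% | 72% | 75% |
| Coverage, those same datasets, value kept | 95% | 95% | 95% | 95% |
| Mean geometric CV, nothing excluded | 43% | 44% | 44% | 44% |
| Mean geometric CV, worst case | 37% | 38% | 41% | 41% |
| Mean geometric CV, only datasets with a drop | 22% | 22% | 27% | 29% |
| Cut in log half-width, only datasets with a drop | 37% | 40% | 32% | 28% |

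The geometric mean stays centred on the truth here because the exclusion is symmetric and driven only by the rule. Discretionary exclusion need not have that property.

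**4. When a value is really wrong.** Assume one value is too high by a factor of 4. The rule detects it in about 60% of datasets at every n. If the value is always kept, the geometric mean is too high by 4^(1/n) − 1 = 26 / 19 / 13 / 11%. Under the rule, the bias is roughly 7–8% at n = 6, falling to 3% at n = 13.

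**The case against.** The strongest reply is that the SAP has already made the procedure optional. The preamble governs the steps, so step 2e can be read as what follows once the analyst has chosen to apply the test. The rule was fixed before first dosing, excluded values are documented, AUC(0–∞) and half-life exclusions are footnoted, and individual estimates are listed. With 6 to 13 patients, a reader could recompute the summary. The PK summaries are descriptive, compartmental modelling sits in a separate plan, and subgroups below six already get both results.

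Most of this stands, and it keeps the point minor. It does not dispose of the point. The preamble says of the value itself, not only of the procedure, that exclusion is not required, so the two sentences still need reconciling. None of the safeguards promises the summary with the value kept.

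The rule also has merit. Under the factor-of-4 error, the root mean squared error of the log geometric mean is lower with it (0.24 against 0.29 at n = 6; 0.144 against 0.160 at n = 13). The worst-case cost on clean data is small (0.195 against 0.175; 0.126 against 0.119). So a reader might infer that a flagged value should stay in the main summary by default, but the evidence does not support that. It is a trade-off, and the SAP's own rule for n < 6 names neither result as the main one.

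**Conclusion.** The point holds as a minor inconsistency with a cheap remedy. Section 6.6.1 gives two answers on whether a flagged value is excluded. At the size planned for both cohorts, it commits to no result with that value kept. This matters because the bound flags valid values in about 31% of clean datasets at n = 6, falling to 19% at n = 13. Where one is dropped, coverage of the nominal 95% interval is about 66–75%.

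Two stronger readings are tempting and not supported:

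- **That 19–31% of the PK summaries will lose a valid value.** The rate is conditional on the test being run, and the SAP leaves both running it and acting on it to judgement. The documents do not say how often that would happen, so the overall effect lies between none and the worst case of 88–91% coverage.
- **That the 3 SD multiplier is wrong and should be widened.** Holding false flags to 5% would need about 5.3 / 4.4 / 3.9 / 3.8 SD at n = 6 / 8 / 11 / 13. Detection of the factor-of-4 error would then fall from about 60% to 20 / 28 / 34 / 36%.

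The flag rates assume independent log-normal values. The coverage and CV figures add the SAP's 45% CV, and the size of the erroneous value is an assumption made here.

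**What to change.** 1. Reword step 2e so that a value beyond the bound is identified as a candidate for exclusion, in agreement with the preamble.
2. For n ≥ 6 between profiles, whenever a flagged value is excluded, report the geometric mean, 95% confidence interval and geometric CV both with and without it, extending what step 1 already does for n < 6.

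No change to the multiplier is requested, and no rule on which of the two results is the main one.

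The cost is a sentence or two of SAP text and one extra summary table when an exclusion occurs. The downside is that the result with the value kept may show a wider interval or be pulled towards an erroneous value; the result without it stands beside it.
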